6.1.3 Exploratory Efficacy Endpoints

6.1.3.1 Quality of Life

BPI-SF

The BPI-SF pain questionnaire is a validated instrument that is a patient self-rating scale assessing level of pain, effect of the pain on activities of daily living and analgesic use. The BPI used in this study is the short form. The BPI uses simple numeric rating scales from 0 to 10.

The BPI-SF scoring will be provided by two dimensions:

- Pain severity: worst, least, average and current pain (Question 3 to 6);
- Pain interference: general activity, mood, work, walking ability, relations, sleep and enjoyment of life (item A to G of Question 9).

Composite scores of pain severity and the pain interference will be produced by averaging their subscales. To calculate the composite score of severity, all four items should be completed; otherwise, the score will be treated as a missing value. For the interference score, if there are missing items, the score will be prorated as follows:

Prorated score = (sum of item scores)/(number of items answered), as long as more than 50% of the items are answered in Question 9 (i.e., a minimum of 4 of 7 items).

Each score ranges from 0 to 10 with higher scores representing a higher level of pain or interference.

QLQ-PR25

The QLQ-PR25 is a 25-item module designed to assess QoL in prostate cancer patients. It includes scales assessing urinary symptoms, bowel symptoms, and treatment-related symptoms; use of incontinence aids; and sexual active and sexual function. Each score ranges from 1 (not at all) to 4 (very much).

Item scores are summed and transformed to a 0-100 scale, as described in Section 7.4.3.1; higher scores represent higher functioning for the two sexual domains but, conversely, higher scores represent more symptoms (i.e. worse HRQoL) for the symptom scales.

EQ-5D-5L

The EQ-5D-5L is an international standardized nondisease specific (i.e., generic) instrument for describing and valuing health status. It is a measure of HRQoL.

The EQ-5D-5L has 5 domains: Mobility, Self-Care, Usual Activities, Pain/Discomfort and Anxiety/Depression. Each domain has 5 response levels (coded as 1 = no problems, 2 = slight problems, 3 = moderate problems, 4 = severe problems, 5 = extreme problems). In addition, EQ-5D-5L has a Visual Analogue Scale (VAS) that elicits a self-rating by the respondent of his/her health status from the worst health status (0) to the best health status (100).

There should be only one response for each domain. Ambiguous values (e.g. 2 boxes were ticked for a single domain) should be treated as missing values.

FACT-P

The FACT-P questionnaire is a multi-dimensional, self-reported QoL instrument specifically designed for use with prostate cancer patients. It is composed of 27 core items which assess patient function in four domains and 12 prostate-related items, grouped into 5 subscales as follows:

- Physical well-being (PWB): 7 items;
- Social/family well-being (SWB): 7 items;
- Emotional well-being (EWB): 6 items;
- Functional well-being (FWB): 7 items;
- Prostate cancer subscale (PCS): 12 items.

Each item is rated on a 0 to 4 Likert-type scale as: 0=not at all; 1=a little bit; 2=somewhat; 3=quite a bit; 4=very much. For some items a response of “4= very much” is better than a response of “3= quite a bit” (e.g., “I get support from my friends”), while for other items a response of “4= very much” is worse than a response of “3= quite a bit” (e.g. “I have pain”). Before calculating the subscale and global scores, the items for which “4” is worse than “3” must be reversed, by subtracting the response from 4. The reversals are performed in the following:

- PWB: reverse all items (GP1 - GP7);
- SWB: do not reverse any items;
- EWB: reverse items GE1 and GE3 - GE6;
- FWB: do not reverse any items;
- PCS: reverse items C2, P1 - P3, P6 - P8 and BL2.

After reversing proper items, for all FACT-P scales, the higher the score the better the QoL.

Each subscale score is the sum of the scores for the items in the subscale. If there are missing items, subscale scores can be prorated, as long as more than 50% of the items are answered in any given subscale (e.g., a minimum of 4 of 7 items, 4 of 6 items, etc). The score is prorated as follows:

Prorated subscale score = (sum of item scores) * (number items in the subscale)/(number of items answered).

The Table 6 lists each FACT-P item and its appropriate scoring.

The FACT-P total score is the sum of all 5 subscale scores. The total score will be calculated only if the overall item response rate is greater than 80% (i.e., a minimum of 32 of 39 items currently scored in the FACT-P have been answered), and no subscale scores are missing.

A deterioration of QoL is defined as a decrease of at least 10-point in the total FACT-P score from baseline.

Table 6 Scoring of FACT-P items

Item number	Scoring				
	Not at all	A little bit	Somewhat	Quite a bite	Very much
PWB	GP1	4	3	2	1
	GP2	4	3	2	1
	GP3	4	3	2	1
	GP4	4	3	2	1
	GP5	4	3	2	1
	GP6	4	3	2	1
	GP7	4	3	2	1
SWB	GS1	0	1	2	3
	GS2	0	1	2	3
	GS3	0	1	2	3
	GS4	0	1	2	3
	GS5	0	1	2	3
	GS6	0	1	2	3

Item number		Scoring				
		Not at all	A little bit	Somewhat	Quite a bite	Very much
	GS7	0	1	2	3	4
EWB	GE1	4	3	2	1	0
	GE2	0	1	2	3	4
	GE3	4	3	2	1	0
	GE4	4	3	2	1	0
	GE5	4	3	2	1	0
	GE6	4	3	2	1	0
FWB	GF1	0	1	2	3	4
	GF2	0	1	2	3	4
	GF3	0	1	2	3	4
	GF4	0	1	2	3	4
	GF5	0	1	2	3	4
	GF6	0	1	2	3	4
	GF7	0	1	2	3	4
PCS	C2	4	3	2	1	0
	C6	0	1	2	3	4
	P1	4	3	2	1	0
	P2	4	3	2	1	0
	P3	4	3	2	1	0
	P4	0	1	2	3	4
	P5	0	1	2	3	4
	P6	4	3	2	1	0
	P7	4	3	2	1	0
	BL2	4	3	2	1	0
	P8	4	3	2	1	0
	BL5	0	1	2	3	4

In patients with QoL deterioration, the time to deterioration of QoL is defined as the time interval from the date of randomization to the first date a decline from baseline of 10 points or more in the total FACT-P score is recorded.

In patients without FACT-P deterioration, the time to deterioration of QoL will be censored on the date of the last FACT-P total score is calculable. Patients with no baseline FACT-P total score and patients with no post baseline FACT-P total score, time to deterioration of QoL will be censored on the date of randomization. Patients entering the open-label phase without deterioration would be censored on the date of last FACT-P assessment prior to first open-label treatment.

6.1.3.2 Time to Pain Progression:

Pain progression event is defined as an increase of $\geq 30\%$ from baseline in the average BPI-SF item scores (pain severity dimension). An alternative definition for the pain progression event will also be used which is defined as increase of ≥ 2 points from baseline in the score at a post-baseline assessment as compared to baseline in the average BPI-SF item scores (pain severity dimension).

In patients with pain progression event, time to pain progression is defined as time from randomization to the first pain progression event.

In patients with no pain progression event, time to pain progression will be censored on the last visit date where BPI-SF was collected. In patients with baseline score missing or no post-baseline score, the time to pain progression will be censored on the date of randomization. Patients entering the open-label phase without pain progression event would be censored on the date of last BPI-SF assessment prior to first open-label treatment.

6.1.4 Other Efficacy Variables

Not Applicable.

6.2 Safety Variables

Safety will be assessed by evaluation of the following variables:

- Treatment-emergent AEs (TEAEs; frequency, severity, seriousness, and relationship to study drug).
- Clinical laboratory variables (hematology, biochemistry, PSA and testosterone)
- Vital signs (systolic and diastolic blood pressure and pulse rate) and weight
- 12-lead ECG

Treatment-Emergent Adverse Event (TEAE)

A TEAE is defined as an AE that occurs or worsens at any time during the treatment emergent period. The treatment emergent period for double-blind treatment period is defined as the time interval from the first study drug intake up to 30 days after the date of the last dose of study drug, study discontinuation, the start of new antineoplastic therapy or prior to first open-label treatment, whichever occurs first. The treatment emergent period for open-label phase is defined as the time interval from the first open-label study drug intake up to 30 days after the date of the last dose of study drug, study discontinuation or the start of new antineoplastic therapy, whichever occurs first.

If AE start date is the same date as the study start, then it will be considered as a TEAE if the box '*Onset after first dose of study drug taken*' is ticked in the Electronic case report form(eCRF). If a patient experiences an event both during the pre-investigational period and during the investigational period, the event will be considered as TEAE only if it has worsened in severity (i.e. it is reported with a new start date and an increased NCI-CTCAE grade).

AE with both a missing start and stop dates, and AEs with a missing start date but has a known stop date which is on or after the first dose of study drug will be considered treatment-emergent.

AEs will be coded to SOC and preferred term using MedDRA v23.0 (or later version) and severity graded using National Cancer Institute's Common Terminology Criteria version 4.03 (NCI-CTCAE v4.03) for AEs.

Drug-Related TEAE

A drug related TEAE is defined as any TEAE with a causal relationship to study drug as assessed by the investigator in the eCRF (by answering 'YES') or with missing assessment of the causal relationship.

AEs of Special Interest

AEs of special interest are defined in Table 7

Table 7 Selection Criteria for AEs of Special Interest

Event of special interest	Selection based on MedDRA 23.0
Convulsion	Narrow SMQ of 'Convulsions'
Hypertension	Narrow SMQ 'Hypertension'
Neutrophil count decreased	Preferred terms of 'Neutrophil count decreased', 'Neutropenia', 'Agranulocytosis', 'Granulocyte count decreased', 'Granulocytopenia', 'Febrile neutropenia', 'Neutrophil percentage decreased', 'Band neutrophil count decreased', 'Band neutrophil percentage decreased', 'Neutropenic sepsis', 'Neutropenic infection' and 'Neutrophil count abnormal'
Cognitive/memory impairment	All preferred terms under the MedDRA High Level Group Term: 'Mental impairment disorders'
Ischemic Heart Disease	Narrow SMQs of 'Myocardial Infarction' and 'Other Ischaemic Heart Disease'
Other selected cardiovascular events	Narrow SMQs of 'Haemorrhagic central nervous system vascular conditions', 'Ischaemic central nervous system vascular conditions' and 'Cardiac failure'
Posterior reversible encephalopathy syndrome	Preferred term 'Posterior reversible encephalopathy syndrome'
Fatigue	Preferred terms of 'Fatigue', 'Asthenia'
Fall	Preferred term 'Fall'
Fractures	All preferred terms under the MedDRA High Level Group Terms: 'Fractures' and 'Bone and joint injuries'
Loss of consciousness	Preferred terms of 'Loss of consciousness', 'Syncope', 'Presyncope'
Thrombocytopenia	Preferred terms of 'Thrombocytopenia', 'Platelet count decreased'
Musculoskeletal events	Preferred terms of 'Back pain', 'Arthralgia', 'Myalgia', 'Musculoskeletal pain', 'Pain in extremity', 'Musculoskeletal stiffness', 'Muscular weakness', 'Muscle spasms'
Severe cutaneous adverse reactions (SCAR)	Narrow SMQ of 'Severe cutaneous adverse reactions'
Angioedema	Narrow SMQ of 'Angioedema'
Rash	All preferred terms including term 'Rash'

Event of special interest	Selection based on MedDRA 23.0
Second primary malignancies	
Narrow SMQs of 'Malignant or unspecified tumours' customized to exclude preferred terms of 'Congenital fibrosarcoma', 'Congenital malignant neoplasm', 'Congenital retinoblastoma', 'Metastases to...', 'Metastasis', 'Metastatic neoplasm', 'Prostate cancer...', 'Carcinoid tumour of the prostate', and 'Neoplasm prostate'
 
AND (inclusive of)
 
Narrow SMQ of 'Myelodysplastic syndrome'
 
AND (inclusive of)
 
All preferred terms under High Level Term of 'Myeloproliferative disorders (excl leukaemias)'
 
 Note: Non-melanoma skin cancers are excluded (preferred terms of 'Basal cell carcinoma', 'Basosquamous carcinoma', 'Basosquamous carcinoma of skin', 'Keratoacanthoma', 'Skin cancer', 'Skin cancer metastatic', 'Squamous cell carcinoma', 'Squamous cell carcinoma of skin', 'Lip squamous cell carcinoma')
 
 Note: Those selected SPM cases will be adjudicated by medical review, which will confirm the evidence of a second primary malignancy

Note: Second primary malignancy reported as TEAEs of special interest will be presented for the entire duration of the study, not merely for the treatment-emergent period.

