In addition, in a phase 2, open-label, single-arm study (9785-CL-0321) in patients with hormone-naïve prostate cancer, 92.5% (62 of 67) of patients had a ≥ 80% decline in PSA from baseline at week 25. Of the 54 patients who were on treatment for 1 year (week 49), 100% had a ≥ 80% decline in PSA from baseline. Of the 26 evaluable patients with metastatic disease at study entry, the best overall response by 2 years (week 97) was 13 (50.0%) patients with CR, 4 (15.4%) patients with PR, 3 (11.5%) patients with non-CR/non-progressive disease (PD), 2 (7.7%) patients with stable disease, 3 (11.5%) patients with PD and 1 (3.8%) patient was not evaluated. At week 97 (2 years of treatment), 45 of 67 (67.2%) patients had a PSA response ≥ 80%; All 45 (100%) patients who were on treatment for 2 years had a ≥ 80% decline in PSA from baseline.

Lastly, the primary efficacy analysis in ARCHES demonstrated a statistically significant, robust and substantial improvement in radiographic progression-free survival together with clinically meaningful improvements in the key secondary endpoints of time to PSA progression, time to start of a new antineoplastic therapy, PSA undetectable rate and objective response rate and a trend in OS (observed at the time of interim analysis) in favor of enzalutamide plus ADT versus placebo plus ADT treatment. For the secondary endpoints, the ARCHES study demonstrated that enzalutamide prolonged the time to the first symptomatic skeletal event and time to castration-resistance. Assessments of patient-reported outcomes data showed that patients receiving enzalutamide plus ADT in ARCHES had a high baseline level of quality of life, which was maintained over time.

Based on the safety information collected to date in clinical trials and in commercial use, the safety profile experienced by patients remains consistent with the approved product label as well as events that can be seen in patients with prostate cancer. The safety profile in mHSPC patients in this study is expected to be consistent with the established safety profile for enzalutamide. To date, the important identified risks associated with enzalutamide are ischemic heart disease, fall, fracture and seizure.

- CONFIDENTIAL -

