### **7.5 Analysis of Safety**

Safety analyses will be conducted using the safety population and summarized by treatment arms as treated.

Baseline laboratory results will be summarized using descriptive statistics by treatment arms. Worst toxicity grades per subject will be tabulated for selected AEs and laboratory analytes.

- CONFIDENTIAL -

Clinical safety data (including AEs, grade 3 and 4 hematologic and nonhematologic events, clinical laboratory evaluations, vital signs, ECGs and physical examinations) will be summarized by treatment groups using descriptive statistics or frequency distribution as appropriate.

Treatment-emergent period is defined as the duration of the study treatment plus 30 days. AEs occurring in this period are termed treatment-emergent AEs.

Duration of treatment and total dose administered will be summarized by treatment groups. In addition, the number and percentage of subjects with dose reduction will be tabulated.

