7.5.1 Adverse Events

The coding dictionary for this study will be MedDRA v23.0. Treatment-emergent AEs will be coded to SOC and preferred terms using MedDRA and graded using NCI-CTCAE v4.03.

Treatment-emergent AEs will be tabulated alphabetically by SOC and by preferred terms within SOC.

An overview table will include the following details per treatment group and overall:

- Number of TEAEs,
- Number and percentage of patients with TEAEs,
- Number of NCI-CTC grades 3 and 4 TEAEs,
- Number and percentage of patients with NCI-CTC grades 3 and 4 TEAEs,
- Number of drug related NCI-CTC grades 3 and 4 TEAEs,
- Number and percentage of patients with drug related NCI-CTC grades 3 and 4 TEAEs,
- Number of drug related TEAEs,
- Number and percentage of patients with causally drug related TEAEs,
- Number of serious TEAEs,
- Number and percentage of patients with serious TEAEs,
- Number of serious drug related TEAEs,
- Number and percentage of patients with serious drug related TEAEs,
- Number of TEAEs leading to death,

- Number and percentage of patients with TEAEs leading to death,
- Number of drug related TEAEs leading to death,
- Number and percentage of patients with drug related TEAEs leading to death,
- Number of TEAEs leading to withdrawal of treatment,
- Number and percentage of patients with TEAEs leading to withdrawal of treatment,
- Number of TEAEs leading to dose reduction,
- Number and percentage of patients with TEAEs leading to dose reduction,
- Number of TEAEs leading to dose interruption,
- Number and percentage of patients with TEAEs leading to dose interruption,
- Number of drug related TEAEs leading to withdrawal of treatment,
- Number and percentage of patients with drug related TEAEs leading to withdrawal of treatment.

An overview table of the TEAE of interest will describe by the number and percentage of patients with TEAEs of interest per treatment group and overall.

The number and percentage of patients with TEAEs, as classified by SOC and preferred terms will be summarized for each treatment group and overall. Summaries will be provided for:

- TEAEs
- NCI-CTC grade 3 or higher TEAEs
- drug related NCI-CTC grade 3 or higher TEAE
- drug related TEAEs,
- serious TEAEs,
- drug related serious TEAEs,
- TEAEs leading to withdrawal of treatment,
- TEAEs leading to dose reduction,
- TEAEs leading to dose interruption,
- drug related TEAEs leading to withdrawal of treatment,

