- TEAEs, excluding serious AEs, that equal to or exceed a threshold of 5.0% in any treatment group,
- TEAEs leading to death,
- drug related TEAEs leading to death,

The number and percentage of patients with TEAEs, classified by preferred terms by decreasing frequency within the overall group will also be summarized.

The number and percentage of patients with TEAEs that equal to or exceed a threshold of 5.0% in any treatment group, classified by preferred terms by decreasing frequency within the overall group, on a 6 monthly basis (0- <3 months; 3- <6 months; 6- <12 months; 12 months or more). The percentage of patients are calculated based on the number of patients still on treatment at the time point corresponding to the lower limit of the time intervals.

To adjust for the treatment duration, the number of TEAEs per 100 patients-years will be summarized, as classified by SOC and PT, per treatment group and overall. The number of TEAEs per 100 patients-years is calculated as the number of events *100 / (sum of the

treatment emergent period duration of all patients treated in the corresponding treatment group, in years).

The number and percentage of patients with TEAEs, as classified by SOC and preferred terms will also be summarized by maximum severity (reported according to NCI- CTCAE version 4.03).

In the patient count, if a patient has multiple TEAEs with the same SOC or PT, but with different severity, then the patient will be counted only once with the worst severity. However, if any of the severity values are missing then the patient will be counted only once with missing severity. In the AE count, the AEs will be presented in each category they were classified to. An AE can be reported multiple times in the AE module if its toxicity grade changes. Summaries will be provided for:

- TEAEs by NCI- CTCAE
- drug related TEAEs by NCI- CTCAE,
- serious TEAEs by NCI- CTCAE

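### SAP 6.2 does not limit its worsening test to events ongoing at first dose, so a new on-treatment episode at the same or lower grade drops out of the TEAE tables

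*SAP*

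**What the plan says.** SAP 6.2 gives two statements that do not agree.

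- The general definition: "A TEAE is defined as an AE that occurs or worsens at any time during the treatment emergent period".
- The special rule: "If a patient experiences an event both during the pre-investigational period and during the investigational period", then "the event will be considered as TEAE only if it has worsened in severity". The SAP explains worsening as follows: "it is reported with a new start date and an increased NCI-CTCAE grade". Both parts are required.

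Protocol 7.5 defines the treatment-emergent period as study treatment plus 30 days and adds: "AEs occurring in this period are termed treatment-emergent AEs". It sets no grade condition.

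TEAE status then decides what is tabulated. SAP 7.5.1 builds the double-blind overview, SOC and preferred-term, serious, drug-related and maximum-severity tables on TEAEs. The same holds for the special-interest summary ("An overview table of the TEAE of interest will describe by the number and percentage of patients with TEAEs of interest") and the exposure-adjusted summary ("the number of TEAEs per 100 patients-years will be summarized"). SAP 7.5 separately provides a listing of all AEs.

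**The concern.** A grade-increase test is sensible for a condition that is already present when dosing starts. It does not suit discrete or recurrent events. A second fall after an earlier one is a new event, whatever its grade.

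AEs are collected from consent (Protocol 5.5.1), so pre-dose events exist to trigger the rule. Several terms in SAP Table 7 can resolve and recur: fall, fractures, fatigue and musculoskeletal events. The sponsor treats two of them as key risks: "the important identified risks associated with enzalutamide are ischemic heart disease, fall, fracture and seizure". The only Table 7 category reported outside the treatment-emergent period is second primary malignancy.

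At stake is whether the safety tables count every new on-treatment episode of these events, as the protocol definition implies.

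**Working it through.** The plan gives no figure to reproduce. The check is to apply the wording to concrete cases.

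| Before first dose | On treatment | New start date? | Higher grade? | TEAE under the SAP 6.2 special rule | TEAE under Protocol 7.5 |
|---|---|---|---|---|---|
| No fall | Grade 1 fall | – | – | Yes (rule not triggered) | Yes |
| Grade 1 fall, resolved | Grade 2 fall | Yes | Yes | Yes | Yes |
| Grade 1 fall, resolved | Grade 1 fall | Yes | No | **No** | **Yes** |
| Grade 2 fatigue, resolved | Grade 1 fatigue | Yes | No | **No** | **Yes** |
| Grade 1 fatigue, ongoing | Unchanged | No | No | No | No (onset before the period) |
| Grade 1 fatigue, ongoing | Rises to grade 2 | Yes (re-reported) | Yes | Yes | Silent on worsening |

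The two documents disagree only in rows 3 and 4: a new episode, after resolution, at the same or lower grade. The SAP's general definition would also count these rows, because the episode occurs in the period.

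**Does another rule bring these events back?** I found none.

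- SAP 7.12.1 sends AEs to the data review meeting only when the onset date is missing or partial.
- SAP 6.2 counts an AE with both dates missing as treatment-emergent, while one with a known on-treatment onset can be excluded.
- The SAP does not define the pre-investigational period, so it is unclear whether medical history counts. It does not say whether matching is by preferred term or reported term.
- Protocol 5.2.2 collects a CTCAE grade in medical history only for conditions ongoing at consent. A resolved earlier condition may have no grade to compare with.

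**Size.** For one term, patients losing a TEAE = N × s × r × g. Here s is the share with the event before dosing, r the share of those with a new episode on treatment, and g the share of those with no episode at a higher grade. The documents give N (120 and 60 planned) but none of s, r or g. As pure assumption, take s = 5–15%, r = 30–50% and g = 80%:

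- Low: 0.05 × 0.30 × 0.80 = 1.2%, or 1.4 of 120 and 0.7 of 60.
- High: 0.15 × 0.50 × 0.80 = 6.0%, or 7.2 of 120 and 3.6 of 60.

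This range illustrates a common recurrent symptom and should not be attached to falls or fractures. With s = 5–20% and r × g = 20–50%, it becomes 1–10%, which shows how far the result depends on the inputs.

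**Direction.** If the same fraction d of events is removed in each arm, the ratio is unchanged and the difference is multiplied by (1 − d). Take the fall rates in Protocol 1.3, 8.8 and 4.7 per 100 patient-years (ratio 8.8 / 4.7 = 1.87, difference 4.1):

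- d = 5% (assumed): 8.36 and 4.47; ratio 1.87, difference 3.9.
- d = 10% (assumed): 7.92 and 4.23; ratio 1.87, difference 3.7.

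**The case against.** The strongest defence is that only continuing events were meant. SAP 7.5.1 says an AE can be entered again when its toxicity grade changes. A new start date with a higher grade is therefore how the eCRF records a continuing event that gets worse. On this reading, the general definition covers a separate new fall, and the special rule covers only events that span first dose. This is plausible, and it makes a drafting slip more likely than a deliberate choice. It does not settle the matter: the sentence is triggered by an event in both periods, not by one ongoing across first dose, and a programmer following its only-if wording would exclude the new episode.

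Other points on that side stand:

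- A reader might extend the problem to convulsion and syncope, which are also in Table 7. Exclusion criteria 15 (seizure history) and 16 (loss of consciousness within 12 months before day 1) largely rule these out, leaving mainly presyncope.
- Many ADT-related symptoms at entry, such as fatigue, are continuing conditions, for which a worsening test is appropriate.
- A discrete event that starts and resolves within a 28-day screening period and later recurs should be uncommon.
- The affected events remain in the AE listing, and expedited SAE reporting under Protocol 5.5.5 is unchanged. A serious recurrence leaves the TEAE tables only if the earlier episode was already at the same or a higher grade.

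**Conclusion.** The point holds as a defect in a stated rule. Followed literally, SAP 6.2 leaves new on-treatment episodes at the same or lower grade out of the double-blind TEAE and AESI tables and the exposure-adjusted rate. This contradicts its own general definition and Protocol 7.5.

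The reach is limited to patients with the same event before dosing. The size cannot be computed from the documents, and the ranges above are assumptions. The expected effect is lower TEAE counts in both arms and some shrinkage of the absolute difference.

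A reader might infer that the rule substantially hides an enzalutamide excess. The documents do not support that. Randomisation balances pre-dose events in expectation, similar proportional removal roughly preserves the ratio, and any episode more severe than the earlier one is still counted. More events could be lost on enzalutamide in absolute number if recurrences are more frequent there, but nothing in the documents shows a larger proportion lost.

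Whether the rule applies to the open-label summaries in SAP Appendix 3 is not stated.

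**What to change.** Replace the special rule in SAP 6.2 with wording to this effect: *An AE or condition ongoing at first dose is treatment-emergent only if its CTCAE grade increases during the treatment-emergent period. An AE with onset in that period, after an earlier episode has resolved, is a TEAE whatever its grade.*

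In the same edit, define the pre-investigational period, state the level at which events are matched, and say whether the rule applies to the open-label phase.

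The cost is one short SAP revision and a derivation from AE start and stop dates that the plan already uses. SAP section 1 allows version-controlled revisions before database hard lock and requires later changes to be justified in the study report. The downside is that TEAE counts rise slightly in both arms. If only continuing events were intended, the edit simply records that intent.
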